3.5. Withdrawal Criteria

Participation in the study is fully voluntary. Study participants can withdraw from the study at any time without comment or penalty. The decision to participate will in no way impact upon their present or future care. In addition, study participants may be withdrawn from the study

solely at the discretion of the Investigator or nominee. The investigator can withdraw a subject from the study for (1) they decide that it is in the patient's best interests due to urgent medical reasons or (2) if a protocol violation occurs or (3) if the patient requests withdrawal. Withdrawn patients will not be replaced in this study.

The reasons for discontinuation/withdrawal will be recorded in the study participant's Case Report Form (CRF). Any study participant(s) withdrawn from the study prior to their completion for any reason will have data compiled to the point of discontinuation to be used for analysis.

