5. STUDY DESIGN

5.1. Summary of Study Design

This is a 2-arm, prospective, randomized, parallel-group, open-label, longitudinal study that lasts 30 days for each study participant. Assessment of primary and secondary outcomes have been planned in an exploratory setting.

Fig. 1 shows the study protocol.

Table 1 shows trial plan and procedure to be conducted on each study visit.

2. Description of study visits:

a) Pre-screening, consenting process, and screening procedures

Potential subjects will be identified through (i) direct advertisement such as posters to be put up around NUS / NUH, (ii) indirect – through word or mouth or snowballing. Participants who are interested will be interviewed over the phone by the study's Clinical Research Coordinator (CRC). During the telephone interview, participants will be given a brief description of the study design and procedures to be followed. If the participant is eligible, with their verbal agreement, arrangement will be made for them to visit NUHS IMU (located in NUS MD6, level 7) for a screening and enrolment visit.

b) Informed consent

Informed consent will be taken by the PI. The study will be explained to the participant in detail. This will be performed in the privacy of a closed-door room. During the consenting process, the study will first be explained to the participants and ample time will be provided for patients to read through the informed consent form. They will also be (i) given opportunity to clarify any doubts before acknowledging the consent form; (ii) allowed to return home to discuss their participation with their family prior to consenting. Non-English speakers will have the English informed consent form with a short consent form in their language, so that they can understand the purpose of this study and what is required of them. If the participant agrees to participate, the informed consent form will be signed by

the PI and the participant, in the presence of a prescribed witness. In the event that the participant is illiterate, or a short consent form will be used, an impartial witness will be present instead. A copy of the informed consent will be kept by both the PI and the participant. Enrolled subjects will be updated in the Screening and Enrolment Log. Unselected subjects will be documented in the Pre-screening Log.

(c) Screening and baseline data collection

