6. METHODS AND ASSESSMENTS

6.1. Randomisation and Blinding

The study will be open-label since our primary endpoint is an objective pharmacokinetic parameter.

Treatment allocation between the Atorvastatin + Omeprazole and Atorvastatin only arms will be generated by a random allocation sequence using real-time web-based randomization system (IVRS) in a 1:1 ratio. Our desired allocation ratio (1:1) can be achieved using permuted block randomization. Block randomization ensures balance between the 2 groups, in which the order of allocation is chosen at random at the beginning of the block. Block size will be determined by the study team member.

Intervention group 1: Atorvastatin 40mg/day + Omeprazole 20mg/day

Control group: Atorvastatin 40mg/day

We target to recruit 78 patients, of whom 39 patients will be assigned to each of the 2 treatment arms. The pharmacist will dispense the IP to the study participants. Each participant will be supplied 30 tablets of Atorvastatin and those in the intervention arm will receive an additional 30 capsules of Omeprazole during the trial. A total of 60 tablets / capsules will be dispensed to each participant in the intervention arm and 30 tablets to each participant in the control arm. An additional 5 surplus tablets / capsules of each drug will also be supplied to replace any damaged or missing tablets / capsules. Atorvastatin and Omeprazole will all be packaged and coded by the manufacturer. The pharmacist will be provided with the code list and will dispense the IP to each participant based on the unique subject ID for that participant. A CRC will provide a prescription on the day of the study visit and ensure that it is kept at the appropriate storage condition prior to administration.

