6.2. Study Visits and Procedures

The total study duration is 31 days and consists of 2 study visits (Fig. 1). Blood samples will be collected at each timepoint (T1 and T2) for metabolic panel and biomarker measurements. All blood sampling (B) are study activities and not routine medical care.

Study Visit T1 (Day 0)

This will be the screening and enrolment visit. Estimated duration is 90 mins. The following procedures will be performed during this visit:

[figure not shown]
- i) Confirming eligibility and Informed consent taking (30 minutes)
- ii) Completion of demographic + medical + medication history survey (10 minutes)
- iii) Blood sample collection (10 minutes)
- iv) Post-collection health monitoring (20 minutes)
- v) Randomization, distribution of drugs and explain how to take the assigned medications (20 minutes)

Study Visit T2 (Day 30)

T2 will be follow-up visit 30 days after intervention. Estimated duration is 60 mins. The following procedures will be performed during this visit:

- i) Self-reported compliance questionnaire and return of unused drugs if any (20 minutes)
- ii) Blood sample collection (10 minutes)
- iii) Post-collection health monitoring (20 minutes)
- iv) Reimbursement (10 minutes)

Figure 1 SEACOL Study protocol

a. Post Study Follow up and Procedures

There will not be post study follow-up or procedures.

b. Discontinuation Visit and Procedures

The last study visit (T2) should be done if withdrawal occurs. Participants may withdraw voluntarily from the study at any time and for any reason without penalty. This will not affect their routine medical care. If voluntary withdrawal occurs, the participant should be asked to continue scheduled evaluations, complete an end of study evaluation and be given appropriate care under medical supervision until the symptoms of any adverse event resolve or until the participant's condition stabilizes. The PI may also withdraw the patient's participation in the study at any time if they decide that it is in the patient's best interests or if they have other medical problems.

The reasons for withdrawal or discontinuation will be documented in the participant's Case Report Form. In the case of any premature withdrawal from the study, blood samples and study data that have been collected up to the time of withdrawal or discontinuation will be kept and analysed as intention-to-treat analysis.

c. Measurements

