11 SAMPLE SIZE AND STATISTICAL METHODS

11.1 Determination of Sample Size

We aim to assess the effect size of a minimum clinically significant difference in Atorvastatin lactone concentration of 1.68µg/L for the Atorvastatin + Omeprazole group compared to the Atorvastatin monotherapy group. Goh et al. 2023 reported a 1.4 times higher ATVlac in patients who were on ATV + OMP and literature on the pharmacokinetics of ATV reported the C_{max} of ATVlac to be 4.2 ± 2.4 µg/L following oral administration of ATV 40mg. By inference, we expect a ATVlac concentration of $4.2 \times 1.4 = 5.88$ µg/L in the ATV + OMP arm

and this equates to a difference of 1.68µg/L in ATVlac concentration compared to the ATV monotherapy arm. Using a 2-sample t-test at a power (1-beta) of 85% and one-sided significance level (α) of 95%, we will need 30 subjects per treatment arm. To account for 30% drop-out after randomization, we will need to recruit at least 39 subjects per treatment arm and a total of 78 subjects for the study.

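### The 30% dropout allowance multiplies 30 by 1.3 instead of dividing by 0.7, so 39 per arm gives about 81–83% power at the plan's own dropout, not 85%; one-sided alpha is also printed as 95%

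*Protocol*

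**What the plan says.** Section 11.1 of the Protocol, repeated in section 3.1, bases the sample size on a "minimum clinically significant difference in Atorvastatin lactone concentration of 1.68µg/L". It takes the control-arm level and its spread from a published pharmacokinetic figure, which puts "ATVlac to be 4.2 ± 2.4 µg/L following oral administration of ATV 40mg". With a two-sample t-test, 85% power and a one-sided significance level printed as 95%, it arrives at 30 per arm ("of 95%, we will need 30 subjects per treatment arm").

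The dropout allowance follows: "To account for 30% drop-out after randomization, we will need to recruit at least 39 subjects per treatment arm". That number becomes the recruitment target. Section 6.1 says "We target to recruit 78 patients, of whom 39 patients will be assigned to each of the 2 treatment arms", and the randomization text in section 5 gives the same figures.

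Four other places bear on the point:

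- Section 3.5: "Withdrawn patients will not be replaced in this study". Section 3.6 likewise provides for no replacement.
- Section 5.1: "Assessment of primary and secondary outcomes have been planned in an exploratory setting".
- Section 6.2: "The last study visit (T2) should be done if withdrawal occurs".
- Section 11.2 plans a one-sided t-test of the lactone level at the second visit, by intention to treat with multiple imputation of missing data. It states no alpha.

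**The concern.** A loss that occurs after randomization is a fraction of those randomized. The number to recruit is therefore the evaluable number divided by the retained fraction, not the evaluable number multiplied by one plus the dropout rate. The two rules differ noticeably at a rate as high as 30%. If the multiplication was used, the trial falls short of its own 30 per arm under its own dropout assumption, and the stated power does not hold there.

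The alpha label matters for a different reason. A significance level of 95% is a confidence level under the wrong name. It is also the only alpha in the Protocol, because section 11.2 specifies the test without one. Anyone checking the sample size has to work out which value was meant.

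**Working it through.** **Inputs (section 11.1, same in 3.1).** Control mean 4.2 µg/L; ratio 1.4, so 4.2 × 1.4 = 5.88 and the difference is 1.68 µg/L. SD 2.4 µg/L, taken as equal in both arms. Power 85%, one-sided test, 1:1 allocation, dropout 30%.

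**Step 1: reproduce the plan's 30 per arm.**

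Standardized difference: d = 1.68/2.4 = 0.70.

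Normal approximation with one-sided alpha 0.05:

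n = 2(z₀.₉₅ + z₀.₈₅)²/d² = 2(1.645 + 1.036)²/0.49 = 29.3, rounded up to 30 per arm.

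The plan's figure is reproduced. The exact noncentral t calculation needs 31 per arm, and 30 gives 84.95%, which is 85% to rounding. So 30 has no slack to absorb a later shortfall.

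**Step 2: which alpha was meant.**

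One-sided 0.025 would give n = 2(1.960 + 1.036)²/0.49 = 36.6, so 37 per arm (38 by exact t). Only one-sided 0.05 fits the stated 30.

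**Step 3: the dropout allowance.**

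- Rule that yields the plan's figure: 30 × (1 + 0.30) = 39.
- What 39 leaves after 30% loss: 39 × 0.70 = 27.3 per arm.
- What is needed to keep 30: 30/(1 − 0.30) = 42.9, so 43 per arm, 86 in total. Check: 43 × 0.70 = 30.1.
- Shortfall: 43 − 39 = 4 per arm, 8 in total.
- Largest dropout at which 39 still leaves 30: 1 − 30/39 = 23.1%.

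**Step 4: power at the numbers retained** (difference 1.68, SD 2.4, one-sided alpha 0.05). The normal approximation is Φ(0.70·√(n/2) − 1.645); the exact value uses the noncentral t with 2n − 2 degrees of freedom.

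| Evaluable per arm | Normal approximation | Exact t |
|---|---|---|
| 30 (required) | 85.7% | 84.95% |
| 27.3 (39 × 0.70) | 82.7% | 81.8% |
| 27 | 82.3% | 81.4% |

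Against the stated 85%, the loss runs from 85 − 82.7 = 2.3 to 85 − 81.4 = 3.6 points. Comparing like with like, it is 84.95 − 81.8 = 3.15 to 84.95 − 81.4 = 3.55 points by exact t, and 85.7 − 82.7 = 3.0 to 85.7 − 82.3 = 3.4 points by the normal approximation.

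**The case against.** The case for leaving the text alone concerns consequence rather than arithmetic.

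- **The effect is small.** Power stays above 80% and section 5.1 calls the outcome assessment exploratory. Raising the assumed SD by 5%, from 2.4 to 2.52, would lower exact-t power at 30 per arm to 81.8%, about as much as the dropout slip does. This stands as a limit on importance. It does not make the dropout sentence correct.
- **The 85% is attached to 30 per arm, where it is right.** That is literally so. But the next sentence offers 39 as the number that accounts for 30% dropout, and 39 does not leave 30.
- **Withdrawn participants are asked to attend the second visit (section 6.2).** If they do, fewer outcomes are lost. About 30 − 27.3 = 2.7 of the expected 39 × 0.30 = 11.7 dropouts per arm would have to supply a sample to bring the count back to 30. The sample size section takes no credit for this. A sample taken after the drug has been stopped may not reflect 30 days of treatment, so restoring the count need not restore the power.
- **Multiple imputation keeps everyone in the analysis (section 11.2).** The only other lactone sample is taken at enrolment, before the study statin and in participants who have had none for 30 days. It should say little about the on-treatment level, so little information is likely to be recovered. This is an inference from the visit schedule; the imputation model is not in the Protocol.
- **The alpha slip is only a label.** Agreed: the sample size is unaffected and the intended value can be recovered. A statistical analysis plan that is not at hand may state alpha, but the Protocol's printed value is still wrong in two sections.

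**Conclusion.** Both errors are real. The dropout allowance uses the wrong formula: at the plan's own 30% loss, 39 per arm leaves about 27 evaluable, and power is 81.4–81.8% (exact t) or 82.3–82.7% (normal approximation), about 2 to 4 points below the stated 85%. By the plan's own rule the target is 4 per arm (8 in total) too low. The 85% holds only if dropout is no more than about 23%.

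The one-sided significance level of 95% should read 0.05. This is a labelling error with no effect on the number.

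The figures assume an SD of 2.4 µg/L in both arms, no second-visit lactone value from participants who drop out, and little recovery through imputation. The consequence is modest and the trial remains adequately sized by the usual 80% standard, but the sample size justification is wrong as written and should be corrected.

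**What to change.** In sections 3.1 and 11.1, keep 78 participants and restate the power, for example: *With 30% dropout about 27 participants per arm are evaluable, giving about 81% power (exact t-test calculation); 85% power holds only if dropout is no more than about 23%.* Leave the assumed dropout at 30%, since nothing in the Protocol supports a lower figure.

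In the same two sections, replace the significance level of 95% with *one-sided alpha = 0.05*.

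The cost is wording in two sections and a slightly less favourable stated power; no participants or procedures are added. If the sponsor prefers to keep 85% power at 30% dropout, the target becomes 43 per arm (86 in total), eight more participants, and the recruitment figures in sections 5 and 6.1 must change to match.

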11.2 Statistical and Analytical Plans

To avoid potential bias due to exclusion of patients (type 1 error), the effect of intervention will be assessed according to the Intention-to-Treat (ITT) principle, such that every patient randomized in the study will enter the primary analysis. Since we expect dropout of some patients on follow-up assessments, all randomized patients will be included in the intention-to-treat analysis, where missing data will be imputed by a multiple imputation method.

We will compare the atorvastatin lactone level between the 2 treatment arms at the second visit timepoint. A one-sided t-test will be performed using R 4.3.1 software.

No interim analyses will be carried out since the study has a short study duration.

12 ETHICAL CONSIDERATIONS

12.1 Informed Consent

Informed consent will be obtained by the PI who is a qualified practitioner. Co-I or CRC will only assist with the informed consent process. The study will be explained to patients in detail. This will be performed in the privacy of a closed-door room within NUHS IMU. During the consenting process, the study will first be explained to participants, and they will be given ample time to read through the informed consent form. Participants will be (1) given opportunity to clarify any doubts before acknowledging the consent form and (2) allowed to return home to discuss their participation with their family prior to consenting. Non-English speaking participants will have the English informed consent form with a short consent form translated in their preferred language. Hence, the informed consent process gives participants sufficient time to consider their participation in the study by having all their questions answered and allowing them to consult others, such as their physician, as well as give them the option of further discussing with their family members before making a decision. Participants would not be approached in a situation where they may feel compromised, thus preventing coercion and undue influence. If the participant agrees to participate, the informed consent form will be signed by the PI and the patient, in the presence of a prescribed witness. If a short consent form is used or if the participant is illiterate, an impartial witness will be present instead. A copy of the informed consent will be kept by both the PI and the participant.

12.2 IRB review

Each participating institution must provide for the review and approval of this protocol and the associated informed consent documents by the NHG DSRB.

12.3 Confidentiality of Data and Patient Records

The study team would store all research data within the institution. For hardcopy data, they will be stored in designated locked cabinet(s) or room(s) that are accessible to authorized study personnel only. For electronic data, they will be stored in a secured computer that is password protected. The databases will not contain subject identifiers and the data linking subject identifiers and the subject identification codes will be stored separately. When portable media (e.g. CD, USB drives etc.) are used to store the data, subject identifiers are stored separately. Records for all participants, including all source documentations (containing evidence to study eligibility, history, billing information and physical findings, laboratory data, etc.) as well as IRB records and other regulatory documentation will be retained by the PI in a secure storage facility at the institution. All information will be coded, stored in a secure area and treated confidentially. Only the PI, co-I, study administrators and research coordinators will have access to the research data. All data files will be password protected and the study team will have access to the research data. All research data and biological materials (blood samples) will be collected prospectively and kept at the PI's lab at NUS-MD6 Centre for Translational Medicine for up to 6 years, for future research. Collected data and blood samples will be de-identified / coded. The PI and / or delegated CRCs will maintain the source code.

13 PUBLICATIONS

In the event of any publication regarding this study, the data will be de-identified so that the identity of the patient remains confidential. In addition, no identifying information or names will be included in any transcripts, conference presentations, research / industry reports or publications.

14 RETENTION OF TRIAL DOCUMENTS

Records for all participants, including CRFs, all source documentation (containing evidence to study eligibility, history and physical findings, laboratory data, results of consultations, etc.) as well as IRB records and other regulatory documentation should be retained by the PI as original hard copy in a secure storage facility and data stored in computer databases will be kept in secure network drives during and after the project, for up to 6 years. The records should be accessible for inspection and copying by authorized authorities.

List of Attachments

Appendix 1 Study Schedule

Procedure	Screening & enrolment (visit T1)	30-days follow-up (visit T2)
Subject information & Informed consent signature	X	
Verification of inclusion and exclusion criteria	X	
Demographics, medical & medication history survey (D)	X	
Randomisation	X	
Peripheral intravenous blood collection (B)	X	X
Self-reported compliance questionnaire (Q)		X
Oral administration of drugs Atorvastatin or Atorvastatin + Omeprazole	<======>	
Serious/Adverse events (AE/SAE)	<======>	

[figure not shown]
X = experimental procedure; ==> = Intervention.

Timepoint: T1 = Screening & enrolment; T2 = Follow-up after 30 days of intervention

Appendix 2 Study design flow chart

Study flow chart

Figure 2. Study on the Effect of Atorvastatin Co-administered with Omeprazole on statin Lactone (SEACOL)

Appendix 3 Demographic + Medical + Medication history survey

Subject ID:
Date & Time:

1) Age (as of January 2024): _____

2) Gender: Male Female

3) Race: Chinese Malay Tamil

Others (Please specify:

_____)

4) Have you ever been diagnosed with the following? (please tick if applicable)

Liver disease

Kidney disease

5) Do you have any other diagnosed medication conditions? (E.g., High blood pressure, high cholesterol, diabetes, heart conditions etc.)

Please specify:

6) Have you taken any of the following medications in the past 30 days?
(please tick if applicable)

Statin (E.g., Atorvastatin, Rosuvastatin, Simvastatin, Pravastatin)

Omeprazole / Esomeprazole / Pantoprazole

7) Are you taking any medications on a regular basis e.g., every day?

Please specify the name of the medication + dose (e.g., 5mg) + how often you are taking it (e.g., two times a day):

8) Are you taking any supplements, herbal or traditional products?

Please specify: _____

Appendix 4 Self-reported compliance questionnaire

Subject ID:

Date & Time:

Study intervention period (e.g., DD/MM/YY to DD/MM/YY):

1) Have you missed taking your assigned medication(s) on any day(s)?

Yes

No

2) If your answer to Question 1 above is 'Yes', please state how many day(s) you have missed:

You may also circle the dates you have missed taking medication(s) on the calendar below if you remember the dates:

(A monthly calendar will be attached here based on the subject's study intervention period, example shown below)

May 2024						
Sunday	Monday	Tuesday	Wednesday	Thursday	Friday	Saturday
			1	2	3	4
5	6	7	8	9	10	11
12	13	14	15	16	17	18
19	20	21	22	23	24	25
26	27	28	29	30	31	

© BlankCalendarPages.com

3) How many tablet(s) / capsule(s) of each of these medications have you been taking each day? (Indicate 'NA' for the medication you did not receive)

References

Studies on Atorvastatin + Omeprazole on Atorvastatin lactone:

- 2) Turner, R. M., Fontana, V., FitzGerald, R., Morris, A. P., & Pirmohamed, M. (2020). Investigating the clinical factors and comedications associated with circulating levels of atorvastatin and its major metabolites in secondary prevention. *British Journal of Clinical Pharmacology*, 86(1), 62–74. doi:10.1111/bcp.14133

Studies related to giving Atorvastatin to healthy volunteers:

- 1) Cilla, D. D., Whitfield, L. R., Gibson, D. M., Sedman, A. J., & Posvar, E. L. (1996). Multiple-dose pharmacokinetics, pharmacodynamics, and safety of Atorvastatin, an inhibitor of HMG-COA reductase, in healthy subjects. *Clinical Pharmacology & Therapeutics*, 60(6), 687–695. doi:10.1016/s0009-9236(96)90218-0
- 2) Abdelkawy, K. S., Abdelaziz, R. M., Abdelmageed, A. M., Donia, A. M., & El-Khodary, N. M. (2020). Effects of green tea extract on atorvastatin pharmacokinetics in healthy volunteers. *European Journal of Drug Metabolism and Pharmacokinetics*, 45(3), 351–360. doi:10.1007/s13318-020-00608-6

Studies related to giving Omeprazole to healthy volunteers:

